9.3.3 Covariate definition

Patient baseline characteristics such as age, gender, comorbidities, cancer-specific data and comedications will be collected at the index date or from the last recorded value within the baseline period. The presence of characteristics will be assessed from patients' medical and pharmacy data in the baseline period (see Annex 1).

Demographic characteristics

- Sex
- Age
- Race
- Individual DOAC or LMWH used to treat CAT
- Number of days between CAT and first recording of anticoagulation use

Clinical characteristics

- Presence of the following clinical characteristics will be assessed from patients' medical and pharmacy data in the baseline period:
 - **Comorbidities/prior history/risk scores:**
 - Number of days from January 1, 2013 to qualifying CAT diagnosis
 - Cancer type(s) present at CAT diagnosis
 - Metastatic disease at time of CAT diagnosis
 - Active/recent treatment (within 3-months pre- or post-CAT diagnosis)
 - Chemotherapy/immunotherapy
 - Radiation therapy
 - Surgical
 - Initial anticoagulation therapy on day of CAT diagnosis
 - Intracranial bleeding
 - Systemic embolism
 - Deep vein thrombosis
 - Pulmonary embolism
 - Heart failure
 - Hypertension
 - Ischemic stroke/transient ischemic attack
 - Peripheral vascular disease
 - Myocardial infarction
 - Percutaneous coronary intervention
 - Coronary artery bypass grafting
 - Any major bleed

- Major adverse limb events (need for surgical or endovascular revascularization or limb amputation)
- Gastrointestinal bleeding
- Central venous catheter
- Liver disease
- Coagulopathy
- Gastroesophageal reflux disease/heartburn
- Anemia
- Asthma
- Chronic obstructive pulmonary disease
- Sleep apnea
- Smoker
- Alcohol abuse
- Anxiety
- Depression
- Lower extremity paralysis
- Psychosis
- Osteoarthritis
- Diverticulitis
- Crohn's disease or ulcerative colitis
- Active or treated *Helicobacter pylori*
- Hypothyroidism
- Recent major surgery within 12 weeks of index event
- Dementia
- Recent trauma (with 90-days)

- Primary hypercoagulable state (e.g., activated protein C resistance, prothrombin gene mutation, antiphospholipid syndrome, lupus anticoagulant syndrome and other primary thrombophilia (per Read code; ICD-9 or -10 coding provided in Annex 1))
- Prior history of VTE
- Varicose veins
- Chronic venous insufficiency (per Read code or ICD-9 /-10 coding provided in Annex 1)
- Acute coronary syndrome
- Carotid stenosis
- Pneumonia
- Osteoporosis
- Orthopedic surgery

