9.6 Data management

- Raw and processed data files will be maintained by The Institute for Epidemiology, Statistics and Informatics (IfESI) on a secured network assessable server and made available only to members of IfESI's research team.
- IfESI and LIRN have developed standard definitions based on different medical and product dictionaries. All new code sets for hospital discharge diagnoses, in-hospital procedures, GP-recorded clinical diagnoses and prescribed medications and lab tests will be prepared by two physicians from

LIRN and IfESI. Existing and new code sets are reviewed for recentness, accuracy and completeness.

- Database management and analyses will be conducted using Stata 14 (StataCorp LP, College Station, Texas).

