Propensity scores will be estimated based upon commonly used variables and accepted risk factors for differential anticoagulation exposure identified during the baseline period including demographics, comorbidities, laboratory and vital signs and concurrent outpatient co-medication use. All clinical characteristics listed in section 9.3.3 of this protocol will be included in the propensity score model. Given the retrospective nature of the data analysis, the presence of a comorbid disease diagnosis will be identified based upon the recording of the specific comorbid read codes. Missing data for covariates will occur when an existing co-morbidity or co-medication is not recorded in the database. In such case we will assume that the respective patient did not suffer from the respective co-morbidity/did not use the respective co-

Reference Number: RD-SOP-1214
Supplement Version: 7

medication. Information on time varying variables e.g. BMI and smoking status will assumed to be constant unless a different variable entry is recorded. Whenever meaningful, missing data will be presented in separate categories labelled "not stated" or "unknown". No imputation will be performed for potentially missing outcomes/endpoint data. Separate propensity score models will be fit once for the primary analysis and for each subgroup analysis.

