Propensity score matching operates by taking each treated study participant and finding the closest propensity score match among controls within a calliper (or bound). Conventional IPTW assigns a weight of $1/PS$ for treated and $1/(1 - PS)$ for untreated patients, allowing individuals with underrepresented characteristics to count more in the analysis. IPTW can produce inflated variance estimates which can be addressed through a simple stabilization of weights (multiplying propensity scores of each participant by the relative proportion of the specific cohort makes up of the total study population). In observational data, in which the initial differences in treatment groups may be large, these methods can modify the target population, fail to achieve good balance or substantially worsen precision. Overlap weighting assigns weights to each patient that are proportional to the probability of that patient belonging to the opposite treatment group. Specifically, treated patients are weighted by the probability of not receiving treatment ($1 - PS$) and untreated patients are weighted by the probability of receiving the treatment (PS). These weights are smaller for extreme PS values so that outliers who are nearly always treated (PS near 1) or never treated (PS near 0) do not dominate results and worsen precision, as occurs with IPTW. These outliers contribute relatively less to the result, while patients whose characteristics are compatible with either treatment contribute relatively more. The resulting target population mimics the characteristics. Overlap weighting also leads to exact balance on the mean of every measured covariate when the PS is estimated by a logistic regression. Like all PS-based methods, overlap weighting cannot adjust for patient characteristics that are not measured and included in the model for the PS. When initial imbalances in patient characteristics between treatment groups are modest, overlap weighting yields similar results to IPTW. The advantages of overlap weighting are greatest when comparator groups are initially very different. To test the robustness of our conclusions to various methods for confounding adjustment, we will also perform a number of sensitivity analyses e.g. *1:1* matching based on propensity scores.

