Cox proportional hazards regression is a method for investigating the effect of variables upon the time a specified event takes to happen. We will fit Cox proportional hazards regression models (with robust estimators) to compare event rates over time for the rivaroxaban (or any DOAC) and LMWH cohorts in the Xarelto SmPC and CAT guidance cancer type cohorts. As propensity score based methods will be assumed to

Reference Number: RD-SOP-1214
Supplement Version: 7

balance key characteristics of the treatment cohorts, the only independent variable that will be included into Cox regression model will be anticoagulant received (rivaroxaban or DOAC or LMWH). Results of Cox regression will be reported as hazard ratios (HRs) with 95% confidence intervals (CIs).

We will use an intention-to-treat approach to analyze the data in which, patients will be evaluated based on the initial anticoagulant prescription registered and will be followed until endpoint occurrence, end-of-database activity, end of data availability or end of designated follow-up time (3-, 6- or 12-months), whichever comes first. Time from treatment initiation to end of follow-up will then be considered the time at risk. On-treatment analysis (patients will be followed until endpoint occurrence, end-of-database activity, end of data availability, end of designated follow-up time (3-, 6- or 12-months), anticoagulant discontinuation or switch, whichever comes first) will be performed as a sensitivity analysis. No adjustments for multiple hypothesis testing will be performed.

Subgroup analyses

Analysis of the recurrent VTE, any clinically-relevant bleeding-related hospitalization and all-cause mortality outcomes among patients prescribed with rivaroxaban and any DOAC (apixaban, dabigatran, edoxaban, rivaroxaban) versus patients prescribed with LMWH patients for acute CAT will be performed stratifying by cancer subtypes (specific subtypes dependent on available sample sizes). To limit the number of analyses performed (and the impact of multiple hypothesis testing), subgroup analyses will only be performed on the primary effectiveness and safety endpoints (recurrent VTE, any clinically-relevant bleeding-related hospitalization and all-cause mortality).

Further descriptive analyses

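### Section 9.7: the usual robust variance treats the estimated overlap weights as known, so the confidence intervals for all-cause mortality would be too wide

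*Protocol*

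**What the plan says.** All of the following is in the protocol.

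- **Weights (9.7).** Under overlap weighting, "treated patients are weighted by the probability of not receiving treatment ($1 - PS$) and untreated patients are weighted by the probability of receiving the treatment". The propensity score comes from a logistic regression, and "All clinical characteristics listed in section 9.3.3 of this protocol will be included in the propensity score model". That list includes cancer type, frailty, laboratory values and "Metastatic disease at time of CAT diagnosis".
- **Balance (9.7).** "Overlap weighting also leads to exact balance on the mean of every measured covariate when the PS is estimated by a logistic regression".
- **Outcome model (9.7).** "We will fit Cox proportional hazards regression models (with robust estimators) to compare event rates over time". On the ground that the propensity score methods balance the cohorts, "the only independent variable that will be included into Cox regression model will be anticoagulant received".
- **Software (9.6).** "Database management and analyses will be conducted using Stata 14".

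No section says that the variance allows for the weights having been estimated. Death from any cause is a primary outcome at 3 months and a secondary one at 6 and 12 months (9.3.2).

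**The concern.** Exact balance on the covariate means does two things. It removes confounding by those covariates, and it removes the chance imbalance in them that would otherwise add noise to the hazard ratio. Where the covariates predict the outcome, the weighted estimate therefore varies less from sample to sample than an unadjusted estimate would.

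The ordinary robust (sandwich) variance does not see this. It treats each weight as a fixed number and so reports roughly the unadjusted standard error. The plan relies on exact balance to justify the treatment-only model, then reports an interval that ignores what the balance does to precision.

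The effect grows with the event rate and with prognostic strength. At 80.0 deaths per 100 person-years (9.5), mortality is the outcome at risk. At stake are the width of its intervals and the power of its tests.

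**Working it through.** **1. The plan's own figures (9.5).** Person-years = 5,600 × 0.6 = 3,360. Multiplying by 0.118, 0.144 and 0.800 gives 396, 484 and 2,688 events, against about 390, 480 and 2,670 stated. Detectable HR = exp(−2 × (1.96 + 0.84)/√events), two-sided 5%, 80% power, 1:1 allocation. This gives 0.753, 0.774 and 0.897, against 0.75, 0.77 and 0.89 stated. The figures reproduce.

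**2. Simulation inputs.** From the documents: cohort sizes of 5,600 (9.5) or 1,000 rivaroxaban with 3,000 LMWH users (section 4), the 9.5 event rates as a guide, logistic propensity score, overlap weights and a treatment-only Cox model. Assumed: prognostic strength, expressed as the SD of the log-hazard linear predictor. Three quantities are compared: the usual robust SE (weights taken as known), a stacked sandwich SE that adds the propensity score term, and the empirical SD of the estimate.

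**3. 12-month mortality, n = 5,600, 1:1, 20 covariates, true HR 1.**

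| Prognostic SD | Robust SE | Stacked SE | Empirical SD | Robust/empirical | Robust coverage |
|---|---|---|---|---|---|
| 0 | 0.0395 | 0.0395 | 0.0405 | 0.98 | 95.1% |
| 0.5 | 0.0408 | 0.0387 | 0.0400 | 1.02 | 95.4% |
| 1.0 | 0.0446 | 0.0388 | 0.0398 | 1.12 | 97.3% |
| 1.5 | 0.0509 | 0.0419 | 0.0433 | 1.18 | 98.3% |

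With no prognostic value the two SEs agree, as they should. In a run with 10 covariates, prognostic SD 1.0 and 2,565 deaths, the robust SE was 0.0407, close to the unadjusted 2/√2565 = 0.0395. The empirical SD was 0.0350 and the stacked SE 0.0347.

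**4. Other settings (robust SE / empirical SD).**

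- 12-month mortality, n = 4,000, 25% treated, 40 covariates: 1.06 (AUC 0.69) to 1.20-1.21 (AUC 0.81). A further run at n = 4,000 with 40-100 covariates gave 1.25, with rejection in 1.2%.
- 3-month mortality, n = 4,000, 25% treated: 1.03-1.04 (AUC 0.64) to 1.08-1.09 (AUC 0.76) with 40 covariates. Further runs with 40-100 covariates gave 1.06-1.12, with rejection in 2.5-3.5%.
- 3-month mortality, n = 5,600, 20 covariates: 1.10 and 1.14 at prognostic SD 1.0 and 1.5.
- Recurrent VTE, n = 5,600: 0.99-1.01 at 3 months and 1.01 at 12 months. Bleeding at 3 months, n = 4,000: 0.97-1.03. Bleeding at 12 months was not simulated; its stated rate (14.4 per 100 person-years) is close to that of VTE (11.8).

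**5. What a ratio r means.** Rejection at HR 1 = 2Φ(−1.96r). For an effect of 2.80 robust SEs (nominal 80% power), actual power is Φ(0.84r) with the robust SE and Φ(2.80r − 1.96) with the correct SE.

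| r | Rejection at HR 1 | Power, robust SE | Power, correct SE |
|---|---|---|---|
| 1.03 | 4.4% | 81% | 82% |
| 1.06 | 3.8% | 81% | 84% |
| 1.12 | 2.8% | 83% | 88% |
| 1.25 | 1.4% | 85% | 94% |

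**6. Does a remedy hold up?** With 100 covariates and a subgroup of 800, the stacked SE was 10% (mortality) and 17% (bleeding) too small, rejecting in 6.5% and 8.1%. The robust SE rejected in 4.4% and 5.3%. With 80 covariates and n = 5,600, the stacked interval covered 92.5% in one mortality scenario. A bootstrap refitting the propensity score gave SE/empirical SD of 0.98 at n = 2,000 (rejection 5.3%) and 1.10 at n = 800 (rejection 3.0%).

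**The case against.** The strongest reply is that the protocol says only that the estimators are robust. It does not define the variance further, and an SAP could name a bootstrap or a stacked form. That is fair as to wording. But 9.7 does fix the class of variance, and its ordinary meaning for a weighted Cox model in a standard package is the fixed-weight sandwich. Read at face value, the stated method gives intervals that are too wide.

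The second reply is about size. The primary time point is 3 months, where the effect is smaller. Prognostic strength is assumed, and some design features could narrow it: recorded palliative care is an exclusion (9.2.3), the comparative cohorts leave out high-bleeding-risk cancers (8.1), and unrecorded comorbidity is coded as absent (9.7). With 100 covariates and prognostic SD 0.5, one 3-month run at n = 4,000 gave a ratio of only 1.02, with rejection in 5.2%. All this stands and limits the point to mortality.

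Three stronger readings are tempting but not supported:

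- **That the treatment-only model is itself the error.** It is not. The weighted estimate already carries the precision gain, and only the reported SE misses it. Adding covariates to the Cox model would change the target: at a conditional HR of 0.89, the simulated estimates were 0.889 conditional and 0.913 marginal.
- **That the study misses its 80% power for death.** In that same simulation (12 months, 10 covariates, prognostic SD 1.0), power was 62% with the robust SE and 73% with the stacked SE. The 11-12 point gap is the variance effect. The rest of the shortfall reflects mainly the marginal HR being nearer 1 than 0.89, not the variance.
- **That this study would be under-weighted in the three-country meta-analysis.** Section 7 says that the studies are meant to be harmonised. If all use the same variance and are inflated by a similar factor, that factor cancels from the inverse-variance weights. Nothing shows that the other two differ.

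**Conclusion.** The point holds for the mortality intervals. Under the usual meaning of a robust variance, the SE is roughly 3-12% too large at 3 months and 6-25% too large at 12 months for moderate to strong prediction of death; single runs gave 2% and 14% at 3 months and 2% at 12 months. By the formula above, tests at the upper ends reject in about 2.8% and 1.4% instead of 5%, and the power lost is about 5 points at 3 months and 8-9 points at 12 months. The loss approaches nil as prognostic strength approaches nil, and it is negligible for recurrent VTE and bleeding.

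This rests on two assumptions: that robust means the fixed-weight sandwich, and that cancer type, metastatic disease, frailty and laboratory values predict death at least moderately well. The error is on the safe side. It causes no bias and no excess of false positives, so the change is worth making but does not affect the validity of the hazard ratios.

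**What to change.** Keep the overlap weights, the treatment-only model and the point estimate. Add to 9.7: *Confidence intervals for the overlap-weighted hazard ratios are obtained by a patient-level bootstrap in which the propensity score model and the weights are refitted in every resample.*

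Do not rely on the stacked sandwich in small subgroups or with about 100 propensity score covariates, where it can be too small. If the bootstrap is unstable in such a subgroup, keep the ordinary robust SE there and say so; a rule for this should be written down in advance.

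The cost is one sentence and computing time. No new data are needed and no hazard ratio changes.

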9.1 Study design

[figure not shown]
We will perform a retrospective cohort analysis using CPRD GOLD and Aurum HES-linked datasets, from January 2013 through latest available data. Patient identification and flow is depicted in **Figure 1**.

Adults diagnosed with active (primary or metastatic) cancer experiencing a hospitalization or emergency department admission or a primary care visit with an incident VTE, being administered rivaroxaban or other DOACs or a LMWH will be included. CPRD and their linked databases do not include information on in-hospital medication use. Patient discharge with anticoagulation supply is routine practice. However, neither the type of AC use, the date of medication start nor the amount of supply are recorded in CPRD or linked databases. Therefore, the first AC recording by the GP, between day 7 and day 30 after index date, will be used to define the type and duration of AC use and to allocate patients with acute VTE to the respective exposure, i.e. DOAC or LMWH. The 7-30 days window has been selected based on previous studies in this population [2, 4]. Subjects will need to be registered with their primary care practitioner (PCP) for at least 12-months prior to the acute CAT event.

Active cancer in this study will be defined as cancer being actively treated, diagnosed within 6-months prior of the index CAT or associated with metastatic disease (regardless of time from initial cancer diagnosis). We will exclude patients with an indication for OAC use to treat other conditions (i.e. atrial fibrillation, prophylaxis after hip/knee replacement in the last three months, stable coronary or peripheral artery disease, long-term VTE prophylaxis) or use of OAC during the 12-months prior to the CAT.

Figure 1: Schematic of VTE analysis

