9.2.1 Study population

The study population of interest will be adults diagnosed with active (primary or metastatic) cancer experiencing a hospitalization or emergency department admission or a primary care visit with an incident VTE, being administered rivaroxaban or other DOACs or a LMWH on or after January 1, 2013. We will identify the first record of anticoagulant therapy between day 7 and day 30 following CAT diagnosis. Subjects will need to be registered with their PCP for at least 12-months prior to the acute CAT event. Patients with cancer diagnoses and/or cancer-specific therapies including chemotherapy, radiotherapy, hormonal therapy and immunotherapy will be identified. Active cancer will be assumed to last 180 days following a cancer diagnosis or therapy recording. Active cancer episodes will be extended for 180 days from the day of the subsequent cancer-specific recording if it is recorded within the initial active cancer episode. Metastatic cancers will assumed to be active ever since first recording.

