9.2.2 Study time frame

We will use CPRD GOLD and Aurum EHR data from January 1, 2013 through latest available data (currently March 2019).

- Patient identification period: The patient identification period will be restricted to January 1, 2013 through latest available data as shown in the figure above.
- Cohort entry: CAT diagnosis, hospitalization or emergency department admission or primary care visit with an incident VTE event.
- Index date: The date of first rivaroxaban (or any DOAC) or LMWH use according to registered prescription 7-30 days after CAT event (new-user design).
- Pre-index eligibility period: Patients will be required to have at least 12-months of EHR registration prior to the CAT event.
- Post-index eligibility period: There will be no minimum post-index eligibility requirement for patient identification.
- Follow-up period: There will be a minimum of 3 months and maximum 12-months follow-up period. Patients will be followed from the first recording of AC use (7-30 days after CAT event) until the end of eligibility.

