We will calculate incidence rates of recurrent VTE, any clinically-relevant bleeding-related hospitalization and all-cause mortality in rivaroxaban patients experiencing CAT regardless of the cancer type and associated bleeding risk. The duration of anticoagulation treatment and discontinuation rates at 3-, 6- and 12-months follow-up will be estimated based on instructions at prescriptions filled in CPRD.

Sensitivity analyses

Various sensitivity analyses will be performed to test the robustness of our study's conclusions. A sensitivity analysis will be performed whereby patients with cancer will need to be admitted to the hospital, emergency department or observation unit for acute DVT and/or PE on or after January 1, 2013 in order to better estimate the "contemporary" comparative effectiveness and safety of the two treatment cohorts/strategies. We will perform 1:1 propensity score matching of rivaroxaban and LMWH patients and

analyze data using a proportional hazards models for the subdistribution of competing risk (competing risk model) to compare event incidences over time for the cohorts. An “on-treatment” approach (patients censored at the first event, anticoagulant discontinuation or switch or end of data availability) will also be performed as the CPRD GOLD and Aurum EHR contain prescription instructions commonly used to identify continuous anticoagulation use. Analysis at 6 and 12-months will be performed.

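### The 'contemporary' sensitivity analysis in Protocol 9.7 starts on the same date as the main cohort, so it restricts care setting and reason for admission but not calendar time

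*Protocol*

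**What the plan says.** **The main cohort.** Section 9.2.2 states: "The patient identification period will be restricted to January 1, 2013 through latest available data". The end of data is given there as currently March 2019. Section 9.2.1 describes adults with active cancer "experiencing a hospitalization or emergency department admission or a primary care visit with an incident VTE"; on treatment, the same sentence requires patients to be "being administered rivaroxaban or other DOACs or a LMWH on or after January 1, 2013". There are thus three routes of entry: hospitalization, emergency department admission and primary care visit.

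**The sensitivity analysis.** Section 9.7, under sensitivity analyses, sets a condition on setting: "patients with cancer will need to be admitted to the hospital, emergency department or observation unit". The condition on reason and date, with the start of the stated aim, reads: "for acute DVT and/or PE on or after January 1, 2013 in order to better estimate the". What is to be estimated is called the 'contemporary' effect of the treatments compared. The protocol gives no later start date for this analysis anywhere.

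**Calendar time elsewhere.** Section 9.3.3 lists the number of days from 1 January 2013 to the qualifying CAT diagnosis among the clinical characteristics. Section 9.7 puts all of those characteristics into the propensity score model. The subgroup analyses in 9.7 are by cancer subtype, not by period.

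**The concern.** The stated purpose of the analysis is about era, but its definition contains no restriction on era. A sensitivity analysis is informative only if the reader knows which feature of the main analysis was changed. Here the label says recent practice, while the feature changed is where, and for what reason, the patient presented. If the result differed from the main one, the difference would come from setting and reason for admission. If it agreed, that would say nothing about recent years.

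The question of era is a fair one for this study. By the protocol's own reference list, the two randomised trials in cancer-associated VTE cited in 9.5 and the ISTH guidance used to define one of the cohorts are dated 2018, late in an identification period that opens in 2013. The analysis named for that question cannot answer it.

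**Working it through.** **1. Windows compared**

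| Feature | Main cohort (9.1, 9.2.1, 9.2.2) | Sensitivity analysis (9.7) |
|---|---|---|
| Start | 1 January 2013 | 1 January 2013 |
| End | latest data, currently March 2019 | no separate end given |
| Setting | hospital, emergency department or primary care visit | hospital, emergency department or observation unit |
| Link to VTE | a contact with an incident VTE | admission for acute DVT and/or PE |

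Taking the end of data as 31 March 2019, the main window is 6 × 365 + 1 (leap day) + 90 = 2,281 days, or 6 × 12 + 3 = 75 months. The sensitivity window is the same. Days removed by the date condition: 0.

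**2. Loosest reading of the date.** In 9.2.1 the date could be read as applying to the anticoagulant record, which falls 7 to 30 days after the VTE, whereas in 9.7 it applies to the VTE admission. On that reading the sensitivity analysis would remove VTEs from at most 30 days of December 2012: 30 / 2,281 = 1.3%. Section 9.2.2 closes even this gap by starting identification on 1 January 2013.

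**3. What is actually removed.** The last two rows of the table differ. Patients entering through a primary care visit drop out. Requiring admission *for* DVT or PE may also drop a VTE that arose during an admission for something else. The protocol gives no split by setting, so neither number can be computed.

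**4. What a real calendar restriction would cost.** First the plan's own figures in 9.5:

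- Expected recurrences: 5,600 patients × 0.6 years × 11.8 per 100 person-years = 396, stated as approximately 390.
- Detectable hazard ratio by the Schoenfeld formula, assuming 1:1 allocation: HR = exp[−(1.960 + 0.842) / √(d/4)]. With d = 390: 2.802 / √97.5 = 0.284, so HR = 0.75, as stated.

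Now take a start of 1 January 2018, purely as an illustration, and assume events are spread evenly over the window:

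- January 2018 to March 2019 is 15 months; 15 / 75 = 20%.
- Events: 0.20 × 390 = 78.
- Detectable hazard ratio: 2.802 / √19.5 = 0.634, so HR = 0.53, against 0.75 for the full window.

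The figure of 78 is generous. It counts recurrences over 12 months in the whole CAT cohort, whereas the primary horizon is 3 months and the comparisons exclude cancers with high bleeding risk. Patients starting treatment after March 2018 would also have less than 12 months of possible follow-up.

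**The case against.** The best defence is that calendar time is already handled: days from 1 January 2013 to diagnosis enters the propensity score, and 9.7 notes that overlap weighting balances covariate means exactly. This stands as far as it goes. Mean diagnosis date will be balanced between arms, so a reader should not infer that confounding by era is ignored. But balance between arms does not show whether the treatment effect differs in later years, which is what a contemporary estimate would have to show.

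A second defence is that this is one sentence among several sensitivity analyses, with the word placed in quotation marks in the protocol, and that no primary estimate or sample size rests on it. That is right and limits the weight of the point. It is still not a detail left to the SAP, because the protocol itself fixes the date, the setting and the purpose, and they do not fit together.

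A third is harmonisation. Section 7 says the protocol is based on OSCAR-US and that a meta-analysis is intended, so changing the population could affect comparability. Whether this sentence came from the US protocol cannot be checked here. Relabelling changes no population, so this argument bears only on an added analysis.

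Some stronger readings are tempting but not supported:

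- *The restriction concentrates the patients with the least certain exposure.* Section 9.1 does say "CPRD and their linked databases do not include information on in-hospital medication use". But exposure is defined in the same way for everyone, from the first GP record on days 7 to 30. No split by setting is given, and nothing says that patients entering through primary care had no hospital-supplied anticoagulant.
- *Only 20% of the patients are recent.* The 20% counts months. The protocol gives no enrolment by year, and March 2019 is described as the current end of data, so a later extract would raise the share.
- *The result will be reported as evidence for current practice.* The protocol makes no such claim.

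**Conclusion.** The point holds. As a calendar restriction the date in 9.7 does nothing: 0 of about 75 months are removed, or at most 1.3% of the window on a reading that 9.2.2 rules out. The analysis is one of care setting and reason for admission, and its stated rationale does not match its definition. No other analysis in the protocol examines whether the effect differs in recent years.

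The consequence is confined to this robustness check; the primary analysis and its sample size do not depend on it. The conclusion rests on the text alone. Only the illustration of precision needs assumptions: data ending in March 2019, events spread evenly over the window, and 1:1 allocation. The number of patients the setting restriction removes is unknown.

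**What to change.** In 9.7, describe the existing analysis as a sensitivity analysis of care setting, restricted to CAT patients admitted for acute DVT and/or PE, and delete 'contemporary' and the rationale attached to it. This is a one-sentence edit with no change to the analysis.

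If the sponsor also wants a contemporary estimate, add it separately: restrict CAT diagnosis to a later start date, keep all care settings, and refit the propensity score within that period. The date is the sponsor's choice, but it should be justified and fixed before analysis.

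The cost of the addition is one more run on existing data and clearly lower precision. At the illustrative 2018 start, roughly 78 of 390 recurrences would remain. It should therefore be presented as an estimate with its interval, not as a test, and the report should note that late entrants have incomplete 12-month follow-up. If harmonisation with the other OSCAR studies matters, the addition should be agreed with them; the relabelling needs no such step.
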